- 8) if antipsychotic treatment is prescribed the plasma concentrations of the drug must be tested and shown to be within therapeutic interval.
- 9) subjects should be judged by the investigator to be lucid and oriented to person, place, time, and situation when giving the informed consent.
- 10) immunoglobulin levels within the normal range

EXCLUSION CRITERIA

- 1) on-going immunomodulatory treatment
- 2) pregnancy or breast-feeding
- 3) weight below 40 kg
- 4) clinically relevant on-going infection
- 5) chronic infections
- 6) positive screening test for hepatitis B, C, HIV or tuberculosis
- 7) any change of psychotropic medication within the previous 4 weeks
- 8) "much" or "very much improved" already at baseline according to CGI-I i.e. scores of 1 or 2 by the clinician
- 9) severe heart failure (NYHA grade IV) or other severe heart disease or history of cardiac

arrhythmia or myocardial infarction

- 10) unable to make an informed decision to consent to the trial
- 11) in compulsory treatment
- 12) treatment with clozapine within the last 2 months
- 13) previous treatments with immunosuppressive agents
- 14) malignancy currently or within 2 years prior to inclusion

STUDY DESIGN

Open pilot study, in addition a qualitative study using content analysis approach.

Participants will be treated initially for 20 weeks and followed for 52 weeks.

STATISTICAL ANALYSIS

Determination of Sample Size

In this pilot study population of 12 participants is presumed to be large enough to determine any effect of rituximab.

Primary objective: Effect of rituximab on schizophrenia symptoms measured with PANSS

The primary outcome (as described in section 5.2) is difference between baseline and endpoint on PANSS scale. 40% reduction in the PANSS scale.

Analyses of laboratory data related to clinical response

Laboratory data will consist of: plasma protein concentrations and leukocyte mRNA expression values for a number of cytokines and related substances (inflammatory markers); total number of B-lymphocytes and number of cells from various B-cell subsets at week 5, 12 and 20, as measured through highly sensitive flow cytometry (HSFC); plasma proteins and lipids as measured through metabolomics analysis; and blood levels of markers for gut permeability.

In order to examine whether baseline characteristics can predict treatment response, baseline values of all these measurements will

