5.2 Outcomes

Primary outcome

The primary outcome measure is change in symptoms measured as change in PANSS score.

Secondary outcome

- Global improvement at week 20, according to a balanced assessment (mean value of three independent assessors: 1) The treating clinician, 2) The patient's self-assessment and 3) A next-of-kin) using the Clinical Global Impression-Improvement (CGI-I) scale (range 1-7; 1 representing "Very much improved").
- Change in Personal and Social Performance Scale (PCP) measuring overall disability
- Change from baseline up to week 20 of illness severity (CGI-S) assessed by the clinician
- Difference from baseline up to week 20 in inflammatory markers in blood (gene expression and proteins) in relationship to clinical response (CGI-I)
- Proportion of responders to treatment, i.e. rated as much or very much improved since baseline according to CGI-I assessed by three different informants: 1) The treating clinician, 2) The patient's self-assessment and 3) A next of kin. If the mean value of these three is below 2.5 then the patient will be regarded as a responder (representing much or very much improved since baseline).

- Safety and tolerability of rituximab during treatment for SSD measured with the questionnaire Any Adverse Reactions (AAR).

Other outcome measures

- B-cell depletion at week 5, and B-cell subpopulations at week 20 in relation to clinical response and baseline levels of B-cells
- Changes in cognitive functioning at 20 weeks:
 - Neuropsychological functioning assessed with e.g. visuospatial and executive tests
- Change from baseline on rating scales that measure psychiatric symptoms specific for each diagnosis (shown below) *during the past 2 weeks*
 - BOCS for measuring obsessive-compulsive symptoms
 - RAADS-R for measuring autistic symptoms
 - PANSS for measuring psychotic symptoms
 - BFCR to measure catatonic symptoms
 - HADS for measuring depressive and anxiety symptoms

Long-term outcomes

40 weeks follow-up:

Outcome measures for long term are identical to that used at 20 week.

Change in symptoms measured as change in PANSS score.

The secondary outcome measures are:

- Global improvement at week 20, according to a balanced assessment (mean value of three independent assessors: 1) The treating clinician, 2) The patient's self-assessment and 3) A next-of-kin) using the Clinical Global Impression-Improvement (CGI-I) scale (range 1-7; 1 representing "Very much improved").

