6.2 Exclusion Criteria

Patients are to be excluded from the trial if any of the following criteria is fulfilled:

- 1) on-going immunomodulatory treatment
- 2) pregnancy or breast-feeding
- 3) weight below 40 kg
- 4) clinically relevant on-going infection
- 5) chronic infections
- 6) positive screening test for hepatitis B, C HIV or tuberculosis
- 7) any change of psychotropic medication within the previous 4 weeks
- 8) “much” or “very much improved” already at baseline according to CGI-I i.e. scores of 1 or 2 by the clinician
- 9) severe heart failure (NYHA grade IV) or other severe heart disease or history of cardiac arrhythmia or myocardial infarction
- 10) unable to make an informed decision to consent to the trial
- 11) in compulsory treatment
- 12) treatment with clozapine within the last 2 months
- 13) previous treatments with immunosuppressive agents
- 14) malignancy currently or within 2 years prior to inclusion

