7.1.2. Rating scales and tests

If more than one clinician will assess the patients rating calibration training for obtaining agreement on scorings will be performed.

Due to the large data collection in combination with the severity of the disorder in these patients missing data will be unavoidable. We will try to avoid missing data by providing clarification if a patient cannot understand the meaning of a question. For each symptom rating scale the response rate is set at a minimum of 80 % of the questions. Isolated missing scores will be replaced with the individual mean.

Demographics

- Background data collection form
- Pans Data Collection Form provides information about inherited physical and psychiatric disorders within the family.

Diagnostic interviews

- Mini International Neuropsychiatric Interview (M.I.N.I. version 7) is a structured clinical interview for psychiatric disorders. In addition the childhood onset diagnoses from the M.I.N.I. kid version will be amended to the adult version of M.I.N.I. (66, 67)
- PsychoNeuroinflammatory Related Signs and Symptoms Inventory (PNISSI) in order to identify and measure symptoms related to neuro-inflammation and diagnose PANDAS and PANS (68)

Assessment of severity, improvement and quality of life

- Clinical Global Impression-Improvement scale (CGI-I) measures change of symptoms on a 7 point Likert scale. CGI-I will also be administered to the next-of-kin (69)
- Patient's Global Evaluation (PGE) provides a self-administered global measure of improvement on a 7 point Likert scale (70)
- Clinical Global Impression-Severity scale (CGI-S) provides a global measure of illness severity on a 7 point Likert scale (69)
- Global Assessment of Functioning (GAF) measures general disability and symptom burden (71)
- Personal and Social Performance Scale (PSP) (72). The PSP is a 100-point single-item rating scale, subdivided into 10 equal intervals. The ratings are based mainly on the assessment of patient's functioning in four main areas: 1) socially useful activities; 2) personal and social relationships; 3) self-care; and 4) disturbing and aggressive behaviours.
- Level 1 Cross-cutting symptom measure of global symptom severity is a patient or informant rated measure included in the DSM-5, which assesses mental health domains that are important across psychiatric diagnoses. It includes 13 domains. We will use it with the clinician's assistance for adults (73)

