7.1.4.8 Qualitative content analysis

The 12 participants from the study will be interviewed about their experiences about participating in the study, using a semi structured interview guide. The questions will be focusing on the participants' experiences about the treatment, the approach from the staff their feelings about their psychiatric diagnosis. Our hypothesis is that the patients may have other thought about their psychiatric condition as it now can be viewed as an inflammatory disorder instead of purely a mental condition. Also we are interested in if the participants have reflected on any change in the approach of the staff since they now are regarded as “somatically ill patients” not simply “psychiatric patients”. The interviews will be transcribed verbatim and analyzed with qualitative content analysis.

Table 1 Study plan

Week		
-4 – 0	Screening prior to treatment with rituximab Decision on inclusion / exclusion	
 • Evaluation of suitability • Vaccination check up (+varicella) • Information to not use attenuated vaccines, what risks are involved and signs of immunosuppression • Consent form • Information card about drug study participation • Demographics questionnaire including FTF-Brief • Treatment history • PNISSI and fine motor examination • Physical examination • Check anti-hypertensive medication* • Test for group A streptococcus • Blood sample • Routine safety: Test of hepatitis, HIV, TB and routine tests • Therapeutic drug monitoring • Urine: illicit drug screen and pregnancy test, inflammatory markers • Assessments (CGI-S and MINI, psychiatric rating scales, GAF, EQ-5D, Level 1 Cross-cutting symptom measure of global symptom severity) • Functioning: PSP and BBQ • Side-effects, AAR • UKU • Client satisfaction questionnaire (CSQ) • Cognitive tests Video recording I • Lumbar puncture (optional) • Faeces biopsy and sample (optional) • fMRI (optional)
0	Baseline Rituximab dose 1000 mg	
 • Assessments (PANSS, CGI-I**, PGE, CGI-S) • Blood sample (inflammatory markers)
2	Nurse check-up	
 • Side-effects, AAR
5, (+/- 1 week)		
 • Side-effects, AAR • Patient evaluated improvement (PGE) • Blood sample (B-cell population)
8	Nurse check-up	
 • Side-effects, AAR • Patient evaluated improvement (PGE)

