10 STATISTICS

10.1 Determination of Clinical response

There is no power calculation due to the nature of this study, a pilot study. If at least 2 patients improve significantly we aim to continue with a controlled study.

Primary outcome

Reduction in PANSS score (30 items) is the primary outcome. 40% reduction in PANSS is regarded as a treatment response.

Secondary outcomes

CGI-I score 1 or 2 which corresponds to much or very much improved at week 20 is regarded as response. Assuming a SD of 1 in our sample we will be able to detect differences between the means before and after treatment corresponding to 0.64 points on the CGI-I scale.

Changes in PSP and clinician rated CGI-S score between enrollment and week 20.

PSP gives a score between 0-100 for disability.

CGI-S is a clinician rated measure of overall clinical severity that is rated on a scale between 1 and 7. This measure also has a floor effect that affects healthy participants, for a person with no clinical complaints or problems (which is most people in a population) will get a score of 1. This floor effect is not relevant to our study population. The score 7, which indicates the highest level of severity is phrased as "Among the most extremely ill patients". This may be true to the patient group in the present study. However, since patients currently in need of compulsory care are excluded from the study, a ceiling effect of the measure is unlikely.

Repeated measures of the PSP and CGI-S will be analysed using a repeated measures ANOVA.

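### Section 10.1 states the detectable CGI-I effect as a before-after difference, although the week-20 CGI-I score is already a rating of change since baseline

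*Combined protocol and SAP*

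**What the plan says.** Section 7.1.2 defines the scale: "Clinical Global Impression-Improvement scale (CGI-I) measures change of symptoms on a 7 point Likert scale". Section 5.2 lists two CGI-I secondary outcomes at week 20. One is the mean of the ratings by clinician, patient and next of kin. The other is the proportion of responders, who are "rated as much or very much improved since baseline according to CGI-I", with a three-rater mean below 2.5.

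Tables 1 and 2 also schedule CGI-I (clinician and next of kin) and PGE (patient) at week 0, the infusion visit. The one stated use of a baseline CGI-I is exclusion 8 in section 6.2, which removes patients who are much or very much improved "already at baseline according to CGI-I i.e. scores of 1 or 2 by the clinician". No reference period is given for that rating.

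Section 10.1 first says "There is no power calculation due to the nature of this study, a pilot study". It then states, for CGI-I, "Assuming a SD of 1 in our sample" and a capacity to "detect differences between the means before and after treatment corresponding to 0.64 points on the CGI-I scale".

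**The concern.** A severity scale such as CGI-S or PANSS measures a state, so an after-minus-before difference is the effect. CGI-I is different: the rater has already made the comparison with baseline. A CGI-I given at week 0 can only describe change over some earlier period. Subtracting it from the week-20 score mixes two periods, and the result is not improvement since baseline.

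Section 10.1 describes exactly that difference, and the week-0 ratings needed to compute it are collected. Section 10.2 does not settle the matter, because it specifies no inference for the continuous CGI-I score. The 10.1 sentence is therefore the only guidance an analyst has for a listed secondary outcome. The problem could spread. Section 10.2.2 uses undefined continuous measures of clinical improvement as the dependent variable in the biomarker models, and section 10.2.4 carries the week-20 methods over to week 40.

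**Working it through.** **Inputs.** From the documents: n = 12 in a single arm (Synopsis); SD 1 and 0.64 points (10.1); the patient's score is the mean of three raters (10.2.1); exclusion 8 uses the clinician's score only (6.2). Assumed, because not stated: two-sided 5% level; 4 is the no-change point, the midpoint of the 1-7 range; all individual scores below.

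**1. Reproducing 0.64.** Half-width of a 95% interval for a mean: t(0.975, 11) × SD/√n = 2.201 × 1/√12 = 2.201 × 0.2887 = 0.635, which rounds to 0.64. So 0.64 is a significance threshold. The two-sided difference detectable with 80% power would be 0.889.

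The same 0.635 arises in two settings:
- A paired difference whose SD is 1. If instead each score has SD 1 and the week-0/week-20 correlation is r, the SD of the difference is √(2(1 − r)). The half-width is then 0.90 at r = 0, 0.78 at r = 0.25, 0.64 at r = 0.5 and 0.45 at r = 0.75.
- The week-20 score alone, SD 1, tested against 4. No week-0 score and no correlation is needed.

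**2. False improvement.** Suppose 8 patients score 5 and 4 score 4 at week 0, and all 12 score 4 at week 20.
- Week-0 mean: (8 × 5 + 4 × 4)/12 = 56/12 = 4.67. Week-20 mean: 4.00.
- Difference: -0.67, beyond 0.64; paired t = -4.69, p = 0.0007.
- Week-20 mean against no change: 4.00 − 4 = 0, with no responders.

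**3. Hidden improvement.** A patient who scores 3 at week 0 and 3 at week 20 contributes 3 − 3 = 0, although the week-20 score is one point on the improved side of 4.

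**4. Sensitivity to pre-infusion drift.** Take the SD of the difference as 1 and no mean change since baseline. The chance that the subtraction gives a significant improvement depends on how far the mean week-0 rating lies above 4:

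| Mean week-0 rating above 4 | Chance of significant improvement |
|---|---|
| 0 | 2.5% |
| 0.25 | 12% |
| 0.5 | 35% |
| 1.0 | 88% |

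**5. Effect of exclusion 8.** Assume clinician week-0 scores follow Normal(4, 1), discretised to 1-7. Removing scores 1 and 2 (6.7% of the distribution) raises the clinician's mean to 4.149, a shift of 0.149. The analysed score averages three raters and only one is screened:
- other two raters uncorrelated with the clinician: 0.149/3 = 0.05;
- all three perfectly correlated: 0.15.

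With SD 0.7 the clinician's shift is 0.033, so the range for the mean is about 0.01 to 0.03.

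**The case against.** The strongest reply is that no before-after CGI-I analysis is planned. The 10.1 sentence concerns detectability and names no test. The repeated-measures ANOVA in 10.1 covers PSP and CGI-S. The ANCOVA list in 10.2.1 omits CGI-I, and 10.2.3 applies difference scores to PSP, CGI-S and the psychiatric rating scales. Section 10.2.1 takes the three-rater mean as the score and cuts it at 2.5, without subtraction. The 0.64 itself needs no week-0 score, so the sentence may be loose wording for a one-sample test. All of this stands, and it limits the point to a defect of specification in one secondary outcome.

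Three stronger readings are tempting and not supported:
- **That the plan commits to a biased contrast.** A reader might infer this from 10.1 together with the week-0 column. The documents never connect the two; the only stated use of a baseline CGI-I is eligibility.
- **That the bias runs only towards benefit.** Section 12.4 accepts that patients may enter in a poor phase, which makes week-0 ratings on the worse side plausible. But exclusion 8 removes only clinician scores of 1 and 2. A patient rated 3 stays in, and step 3 shows that subtraction can then conceal benefit.
- **That exclusion 8 alone adds 0.15, or 23% of 0.64.** That is the clinician's shift. It reaches the three-rater mean in full only if the raters agree perfectly, whereas 10.2.1 calls them independent.

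What the reply does not remove is that the sentence describes the wrong contrast for this scale, and that no other section supplies the right one.

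**Conclusion.** The point holds as a correction to section 10.1. The before-after wording does not fit a scale that already rates change since baseline, and it is the only inference stated for continuous CGI-I. PANSS and the responder proportion are unaffected.

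The size depends on week-0 ratings that the documents cannot supply. Under the assumed scores, subtraction yields -0.67 when nothing changed since baseline, and zero when there was improvement. Drift before the infusion is the main hazard. The tilt from exclusion 8 is small, about 0.05 to 0.15 points under Normal(4, 1) depending on rater correlation, and smaller with a narrower spread. All of this rests on 4 being the no-change point.

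**What to change.** - **Section 10.1:** replace the before-after sentence. Analyse the week-20 three-rater mean CGI-I alone, and likewise week 40, against the scale's no-change point (the sponsor to confirm that this is 4), with a 95% interval. With SD 1 and n = 12 the half-width is 0.635, so 0.64 can remain if it is described as precision around the week-20 mean. On those figures a mean of about 4 − 0.64 = 3.36 or lower would differ significantly from no change.
- **Section 10.2:** name that analysis for continuous CGI-I. State that week-0 CGI-I and PGE enter no efficacy analysis and no biomarker-response model.
- **Exclusion 8 and Table 1:** ask the sponsor to state the period to which the baseline CGI-I refers, and to reconcile it with Table 1, where CGI-I is absent from the screening list and first appears at week 0. The documents do not say whether that period starts at screening or earlier, so the review should not supply one.

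The cost is wording in three places. No data, visits or patients are added.

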10.2 Statistical methods and analytical plan

10.2.1 Primary objective: Improvement reflected in change in PANSS score

To investigate whether markedly ill, treatment-resistant, psychiatric patients according to our inclusion/exclusion criteria are significantly improved after treatment with the immunomodulatory drug rituximab (as addition to the patients' standard treatment).

We will analyse the clinical data on a modified intention-to-treat (ITT) definition basis, i.e. including treatment dropouts who received at least one dose of rituximab as well as completers. In addition, a completer-only analysis will be performed. *The primary outcome* is change in PANSS score, assessed by a clinician.

Secondary outcomes: CGI-I score (range 1-7). All CGI-I ratings are performed by three independent raters (the patient, his or her next of kin and a clinician). The mean value of these three values will be used as the patients' scores. If one of the values is missing, the mean will be calculated using only two values.

One secondary outcome is binary: the proportion of responders to treatment at week 20 (and similarly at week 40). Treatment response is defined as a mean value below 2.5 on the CGI-I (calculated as above), which corresponds to the scale step descriptors "much improved" or "very much improved". Non-response is defined as a mean CGI-I value of 2.5 or higher.

The continuous secondary outcome variables at the 20-week and 40-week end points (CGI-S, PSP, and diagnosis specific rating scales) will be included in analysis of covariance (ANCOVA) models, controlling for baseline measures and demographic variables.

Side-effects will be closely monitored and types, frequency, severity and seriousness will be reported.

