4. Proportion of responders: Three different informants base their CGI-I evaluations on independent assessments: a) The treating clinician, b) The patient's self-assessment and c) A next of kin. If the mean value of these three is below 2.5 then the patient will be regarded as a responder (representing much or very much improved since baseline).
5. Frequency, seriousness and severity of side effects.

Other outcomes:

The other outcome measures are:

1. B-cell depletion at week 5, and B-cell subpopulations at week 20 in relation to clinical response and baseline levels of B-cells
2. Change from baseline to week 20 in

cognitive functioning

3. Change from baseline to week 20 in diagnosis specific rating scales
4. Change in brain activity in fMRI.

Long-term outcomes:

40 weeks follow – up: Primary outcome for long term is identical to that used at 20 week:

1. Change in symptoms measured as change in PANSS score from baseline

The secondary outcome measures are:

1. Difference from baseline up to week 40 in inflammatory markers in blood (gene expression and proteins) in relationship to clinical response
2. Change in Personal and Social Performance Scale, measuring overall disability from baseline up to week 40
3. Change from baseline up to week 40 of illness severity (CGI-S) assessed by the clinician
4. Life quality measured with BBQ
5. Global improvement. Three different informants base their CGI-I evaluations on independent assessments: a) The treating clinician, b) The patient's self-assessment and c) A next of kin

Other outcome measures are:

1. B-cell subpopulations at week 40 in relation to clinical response
2. Change from baseline to week 40 in cognitive functioning
3. Change from baseline to week 40 in psychiatric rating scales

POPULATION

INCLUSION CRITERIA

Twelve psychiatric patients (ages, 18-40).

- 1) patient ages 18 to 40 years
- 2) a duration of illness exceeding 2 years
- 3) correspond to "Markedly ill", "Severely ill"

or "Among the most extremely ill patients" on the Clinical Global Impression – Severity scale (CGI-S)

- 4) Global Assessment of Functioning below 50
- 5) current Diagnostic and Statistical Manual for DSM-5 diagnoses of Schizophrenia spectrum disorder
- 6) treatment resistance, i.e. failing to remit despite adequate treatments
- 7) if female and with any risk for pregnancy, willing to use contraceptives

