Overall, our research group consists of clinical researchers (psychiatrists) with extensive experience of patients with severe psychiatric illness, including children. The PI has worked decades as a senior consultant and currently assess treatment resistant psychiatric patients with SSD, OCD and ASD at the Psychiatric clinic in Örebro on weekly basis. Also [name], psychiatrist, PhD and collaborator in this study, has extensive clinical experience with severe treatment resistant psychiatric patients. Three doctoral students are involved in various projects related to inflammation in psychiatric patients. One of the PhD students, a nurse, is accustomed to perform blood tests in the homes of the patients, thus they don't have to go to a clinic. We closely collaborate with preclinical senior researchers at Therapeutic immune design, CMM, Karolinska institutet and the research group at iRiSC, Örebro University. Our collaborators have extensive experience in working with the research methods needed for our analyses and have long experience of the in vitro systems to be used on whole blood and its components. In the present study we will also collaborate with the Department of Clinical and Experimental Medicine at Linköping University and the Department of Radiology at Örebro University Hospital to conduct an imaging study on inflammation in CNS. We will collaborate with Nutrition-Gut-Brain Interactions Research Centre (NGBI) at Örebro University for research on the effect of rituximab treatment on gut microbiom. For research on metabolic markers we will work together with Man-Technology-Environment research centre (MTM) at Örebro University. For bioinformatics we will collaborate with Faculty of Health, Science and Technology at Karlstad University. Finally, we will collaborate with clinical researchers within the fields of occupational therapy, paediatrics, child and adolescent psychiatry and rheumatology. For health economy analysis we will collaborate with researcher at University health care research centre (UFC) in Örebro.

Clinical significance

In this trial we will study rituximab in markedly ill psychiatric patients diagnosed with schizophrenia spectrum disorder and with considerable impairment. Regularly they are treated with high dosages of psychiatric drugs nevertheless they suffer from symptoms as well as significant side effects.

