12.3 Risk/benefit assessment

Patients will share personal information, which could be perceived as intrusive. However, all collected data will be coded and data will only be presented at a group level. Blood sampling and lumbar puncture can cause pain, but only for a brief period. The fMRI and gut examination can be experienced as difficult but it is not painful or dangerous. Handling urine and faeces samples may cause discomfort in the patient. In this study, only blood samples collected at baseline and week 20, in addition to responses to questionnaires at baseline and week 20 for assessment of outcome, are mandatory for participation.

The patients' expectations of the study and its intervention may be high, which can generate disappointment among those who do not experience a positive effect from the study drug.

Side effects of rituximab treatment may occur, some of those can be serious, but rituximab is usually well tolerated. Among patients with rheumatoid arthritis, even mild side effects are reported to be rare. According to the Summary of Products Characteristics (SmPC), between 1/100 and 1/1000 patients report depression and/or increased nervousness as a side effect from rituximab. The prevalence for these side effects is unknown among psychiatric patients. However, all side effects will be carefully documented in the present study. If the patient becomes depressed or severely anxious discontinuation of the study drug should be considered. Rituximab is a standard treatment for multiple sclerosis and rheumatoid arthritis in Sweden. Approximately 5,000 patients with rheumatoid arthritis is treated with MabThera (48/100 000) and as MabThera is prescribed off label for MS another 5 to 15,000 patients receive this treatment yearly for this indication (227/100,000 are diagnosed with MS, Danish data). In Örebro, rituximab is administered to the rheumatoid arthritis patients on a day-ward at Örebro University hospital, run by specially trained nurses.

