The side effects of rituximab include infusion reactions, severe skin and mouth reactions, hepatitis B virus reactivation and in extremely rare cases (1/25000 in patients with rheumatoid arthritis (102), progressive multifocal leukoencephalopathy (PML), a serious brain infection caused by the JC virus. We will collaborate with a senior rheumatologist who is experienced with rituximab. Since the treatment may activate latent infections, all patients will be screened for hepatitis and HIV prior to the study. The patients will be pre-medicated to reduce the risk of infusion-related side effects, and they are carefully monitored during the course of the study.

The reason to not use a standard drug for inflammation, such as cortisone, is because it may induce mania in susceptible individuals and is therefore not suitable for psychiatric patients.

We will film the patients on three different occasions. This is because we want to be able to show the patient if there is a treatment effect or not. It may also enable a completely external assessment of treatment effects. Since rituximab has not been tested in trials of psychiatric disorder an effect of the drug can be questioned. In such case we possibly could show video clips of treatment effects, if the patient allows it (but this is not included in this study). The film clips may also support a request for further treatment with the drug.

Early onset of severe psychiatric disability is associated with a particularly poor long-term prognosis. This is often the case for schizophrenia. Delayed treatment may cause persistent brain damage if associated with inflammation in the brain (which is presumed). We believe that earlier treatments may have better effects on the symptoms than treatment that are first provided after many years with the disease. Also, rituximab is frequently used for treating children and adolescents with MS (103). Thus it would be unjust to exclude them from participation in a trial with a medication that may prove helpful.

The patients will remain on their standard psychiatric treatment throughout the course of the study and are allowed to adapt their medication dose accordingly. Therefore, we do not put the patient's mental health at risk. The side effects of rituximab do not coincide with those that can be expected from psychiatric medication (apart from possibly clozapine), which implies low risk for add-on side effects.

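### The AAR and UKU taken before rituximab enter no planned analysis, so reported side-effect frequencies may mix pre-existing with treatment-emergent complaints

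*Combined protocol and SAP*

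**What the plan says.** Safety and tolerability is a stated objective. The synopsis lists the matching secondary outcome as "Frequency, seriousness and severity of side effects", and section 5.2 words it as "Safety and tolerability of rituximab during treatment for SSD measured with the questionnaire Any Adverse Reactions (AAR"). Neither version refers to a pre-treatment value.

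Tables 1 and 2 place both instruments at screening (weeks -4 to 0). After dosing, the AAR is repeated at the follow-up visits and the UKU at weeks 20 and 40. Section 9.1 places the UKU at endpoints 1 and 2 and does not mention the screening UKU.

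The only sentence on side effects in the statistics section is in 10.2.1: "Side-effects will be closely monitored and types, frequency, severity and seriousness will be reported". It names neither instrument; the link to the AAR and UKU comes from sections 5.2, 7.1.2 and 9.1. Section 9.1 adds that adverse events observed from dosing onward will be recorded, analysed and summarised.

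The design is given as "Open pilot study, in addition a qualitative study using content analysis approach", with "Twelve psychiatric patients (ages, 18-40"). On the background state of these patients, section 4.1 says that despite high doses of psychiatric drugs "nevertheless they suffer from symptoms as well as significant side effects".

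**The concern.** With no control arm, a frequency of complaints after dosing can be read only against what the same patients reported beforehand. The trial collects that information and then gives it no role. The clinical scales are treated differently: sections 10.2.1 and 10.2.3 plan change scores and baseline-adjusted ANCOVA for PSP, CGI-S and the psychiatric rating scales. The AAR and UKU appear in none of sections 10.2.1 to 10.2.4.

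The protocol itself expects a background. Patients enter with symptoms and drug side effects, and section 12.3 notes that between 1 in 100 and 1 in 1,000 patients "report depression and/or increased nervousness as a side effect from rituximab" and that the prevalence of these effects in psychiatric patients is unknown. What is at stake is whether the tolerability result can be interpreted. It matters beyond this pilot, because section 10.1 foresees a controlled study if at least 2 patients improve.

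**Working it through.** The documents give no rate, precision or sample-size figure for side effects, so there is no stated number to reproduce. The check has two parts.

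**1. Where the screening values could be used**

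| Place | AAR/UKU at screening | Use of the screening value |
|---|---|---|
| Tables 1 and 2 | both scheduled | none stated |
| Section 5.2 | not mentioned | none stated |
| Section 9.1 | not mentioned; UKU at endpoints 1 and 2 only | none stated |
| Section 10.2.1 | not mentioned | side effects reported descriptively |
| Sections 10.2.2 to 10.2.4 | not mentioned | none |

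**2. How much this could matter (illustration)**

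Inputs: n = 12 and the 48 UKU items (section 7.1.2) come from the documents. The background prevalence p of a complaint before dosing is not given and is assumed to lie between 5% and 50%. The rate q at which a patient without the complaint develops it after dosing is also assumed. A complaint present at screening is taken to persist without worsening.

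- Tally ignoring screening: 12 × [p + (1 − p)q]
- Tally of new complaints only: 12 × (1 − p)q
- Chance that at least one of 12 patients has the complaint with q = 0: 1 − (1 − p)^12

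| p | Tally ignoring screening, q = 0 | New only, q = 0 | Tally ignoring screening, q = 10% | New only, q = 10% | P(at least 1 of 12), q = 0 |
|---|---|---|---|---|---|
| 5% | 0.6 | 0 | 1.74 | 1.14 | 46% |
| 10% | 1.2 | 0 | 2.28 | 1.08 | 72% |
| 20% | 2.4 | 0 | 3.36 | 0.96 | 93% |
| 30% | 3.6 | 0 | 4.44 | 0.84 | 99% |
| 50% | 6.0 | 0 | 6.60 | 0.60 | >99.9% |

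For example, at p = 5% and q = 10%: 12 × (0.05 + 0.95 × 0.10) = 12 × 0.145 = 1.74, of which 12 × 0.95 × 0.10 = 1.14 are new.

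If every UKU item had the same prevalence, the expected number of the 48 items present in at least one patient with no drug effect is 48 × [1 − (1 − p)^12]: about 22 at 5%, 34 at 10%, 45 at 20%, 47 at 30% and 48 at 50%.

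Across the assumed range, the tally that ignores screening is driven mainly by p once p is well above q. At p = 50%, 6.0 of the 6.6 patients counted had the complaint before treatment.

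**The case against.** The strongest reply is that the plan states no faulty counting rule and has safeguards. A reader might infer that illness and psychotropic complaints are counted as rituximab side effects. The documents do not say so; the handling of AAR and UKU items is undefined. Section 9.1 also registers adverse events only from dosing, asks at each visit about symptoms new since the last visit and about previous side effects that have eased or increased, asks the patient about a link to rituximab, and requires the investigator to rate relatedness. These steps do separate new, worsened and unrelated events, and that part of the reply stands. It does not close the gap: they act on individual adverse events and do not say how AAR and UKU frequencies are tabulated. The relatedness rating is unblinded, and 10.2.1 does not list it among what will be reported.

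Two other inferences fail. A reader might suppose that the checklists do not ask about onset, but neither form is reproduced, so this cannot be known. A reader might also think that section 12.3 contradicts itself where it says "The side effects of rituximab do not coincide with those that can be expected from psychiatric medication". That sentence concerns psychiatric medication, with a reservation for clozapine; overlap with symptoms of the illness is a different matter and does not refute it.

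Depression and anxiety do have a planned baseline comparison, through HADS at weeks 20 and 40. A group-level worsening there could be seen. This does not extend to the other AAR and UKU items or to the visits in between.

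Finally, the prevalence range is an assumption. At its lower end the excess is below one patient per complaint.

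**Conclusion.** The point holds as a gap in the analysis plan: the pre-treatment AAR and UKU are collected but unused, so the reported frequencies may mix pre-existing with treatment-emergent complaints. Under an assumed prevalence of 5% to 50%, stable complaints and no drug effect, the mixing amounts to 0.6 to 6 of 12 patients per complaint. The contrast with 0 for new-or-worsened counting depends on that stability. Section 12.4 notes that symptoms fluctuate, so some new or worsened complaints would appear without any drug effect, and such counts in a single arm still do not prove causation. The change should be made because it decides what the safety objective can conclude and uses data already scheduled.

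**What to change.** In section 10.2.1:

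- Report each AAR and UKU item as new versus screening, or as worsened where the item is graded.
- Show the screening frequency beside the frequency at each post-dose visit at which the instrument is used.
- Give paired UKU shift counts from screening to weeks 20 and 40, among patients with both assessments.
- Keep the raw post-dose counts in a listing.
- Report all adverse events and those rated as related separately.

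Reconcile section 9.1 with Tables 1 and 2 on when the UKU is taken, and state the purpose of the screening assessment.

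The cost is mainly table specification, since no extra visit or measurement is needed. One point must be checked: the documents do not show whether AAR items are graded. If they are not, the AAR can support only the new-versus-screening classification. The downside is that headline frequencies will be lower, which is why the raw counts should stay available.
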